2 PARTICIPANTS

2.1 Participants. Describe the general characteristics of the subject populations or groups, including age range, gender, health status, and any other relevant characteristics.

Participants will include children of all genders, ages 12-36 months, with diagnoses of cerebral palsy or who are at risk for cerebral palsy, and their parent or legal guardian of all genders ages 18 and above.

2.2)Inclusion and exclusion criteria.

a. Inclusion criteria. Describe the specific criteria that will be used to decide who will be included in the research from among interested or potential subjects. Define any technical terms in lay language.

Inclusion criteria for the study: 1) The child will be between 12-36 months old; 2) have a medical diagnosis of CP with any level (I-V) of associated motor ability according to the Gross Motor Function Classification System (GMFCS) or be at risk for CP according to birth history and current developmental status; 3) be able to attain a seated position with or without support; 4) be able to tolerate upright sitting with or without support while moving through space for 30 minutes; 5) and live in a household where English is spoken proficiently; Adults will 1) be 18 years or older and be the legal caregiver for the child participant; and 2) demonstrate proficiency in English. Inclusion criteria will be secured via caregiver report using screening questions.

b. Exclusion criteria. Describe the specific criteria that will be used to decide who will be excluded from the research from subjects who meet the inclusion criteria listed above. Define any technical terms in lay language.

Children will be excluded from the study if: 1) they have not been given a medical diagnosis of CP or are not at risk for CP (per parent report of birth history and current developmental status); 2) if they cannot attain a seated position with or without support; 3) if they cannot tolerate upright sitting with or without support for 30 minutes; 4) all participants will be excluded if they are not proficient in English (determined per screening process).

2.3 Prisoners. IRB approval is required in order to include prisoners in research, even when prisoners are not an intended target population.

a. Will the proposed research recruit or obtain data from individuals that are known to be prisoners?

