Research Design and Timeline: We will conduct our work using a mixed-methods, counterbalanced AB crossover design, where intervention A is use of the Explorer Mini, and intervention B is use of the modified ride-on car. All participants at all sites will undergo the same research procedures. Participants will receive both powered mobility interventions, and randomization into two groups at each site will occur to determine which intervention participants will receive first (Modified ride-on car: n = 3; Explorer Mini: n = 3). Three research visits will be scheduled during the study. Baseline assessment (T0) will consist of initial device training and safety checkoff, interview, and administration of outcome measures. Intervention phase 1 will take place for 8 weeks, followed by a mid-study assessment (T1) at which time interviews and outcome measures will be repeated and parent perception/satisfaction with device will be assessed. Training and safety checkoff on the second device will occur. No washout period between devices is indicated because both devices provide self-initiated mobility. Intervention phase 2 will take place for 8 weeks, followed by the final study assessments (T2), where devices will be removed from the participants' homes and a final set of interviews and outcome measures will be administered. During each 8-week study phase, the researchers will conduct two virtual check-ins with each family to answer questions and provide support and standard activity suggestions for device use (i.e. open exploration, switch/joystick play, goal-directed driving).

Equipment:

Modified Ride-On Cars. Commercially available, off-the-shelf, battery-operated rideon toy cars will be modified. *Switch activation*. Unmodified, a child uses their foot to press a pedal or their finger to press a small switch located on the steering wheel to activate the ride-on car which is difficult for young children with CP. Modifications of ride-on cars will include installation of an easy-to-press switch that has a large surface area and responds to a light touch for activation. *Seating support*. Common materials, such as PVC pipe, swimming kickboards, and Velcro will be used to build a

customized supportive seating system. Seatbelts are added in all cars, and fivepoint harnesses are available if needed for appropriate postural support. Cars

Figure 1. Child with CP using a modified ride-on car.

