ID: STUDY00011386 Early Powered Mobility for Toddlers With Cerebral Palsy Using the Permobil® Explorer Mini and a Modified Ride-On Car

Statistical Analysis Plan Document Date: 12/1/2020

Statistical Design and Power

Data Analysis:

All statistical analyses will be conducted using SPSS (version 26.0 IBM, Armonk, NY). Descriptive participant characteristics (e.g., age, sex, race/ethnicity, CP subtype, GMFCS-level) will be summarized as categorical variables.

Aim 1: Developmental, activity and participation outcomes

Sample size justification: Since the current proposal is a pilot study, there are no previous data to conduct a power analysis on the potential change of developmental, activity and participation outcomes as a result of using different powered mobility devices.

Analysis for measures assessed in Aim 1 will include descriptive statistics. Data will be assessed for normality and symmetry. If normality assumptions are met, we will use parametric statistics to examine between- and within-subject effects. If assumptions are not met, we will use the non-parametric equivalent of the planned analyses. We will calculate three separate analyses to examine changes in_developmental, activity and participation outcomes. (1) Separate 2 (group: 1, 2) x 3 (time: T0, T1, T2) repeated measures MANOVAs will be calculated to determine between- and within-subject changes on mean scores of developmental, activity and participation outcomes. (2)_Stratification into low and high usage groups will occur based on mean device use data. We will use these stratified groups to run our analyses to determine if device use is related to developmental, activity and participation outcomes. Separate 2 (group: low usage, high usage) x 3 (time: T0, T1, T2) repeated measures MANOVAs will be calculated to determine between- and scores of developmental, activity and participation outcomes. Separate 2 (group: low usage, high usage) x 3 (time: T0, T1, T2) repeated measures MANOVAs will be calculated to determine between- and within-subject changes on mean scores of developmental, activity and participation outcomes. Post-hoc analyses (i.e. Bonferonni correction) will be used for the above analyses to control for the type I error rate and determine where the significant differences exist. (3) We will also use visual analysis to determine if clinically significant differences exist.

Aim 2: Use patterns (frequency, duration, environment) & families' perspective and experiences

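### Age at entry (12 to 36 months) is in neither set of Aim 1 models: it can confound the non-randomised low/high-use comparison, and in the randomised order comparison it costs precision at most.

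*SAP*

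**What the plan says.** Protocol section 2.2 sets the entry age: "The child will be between 12-36 months old". The SAP's Data Analysis paragraph names age only among the characteristics to be tabulated: "Descriptive participant characteristics (e.g., age, sex, race/ethnicity, CP subtype, GMFCS-level) will be summarized as categorical variables".

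The SAP's Aim 1 section then gives two sets of models. The first compares the order groups: "Separate 2 (group: 1, 2) x 3 (time: T0, T1, T2) repeated measures MANOVAs will be calculated". The second compares use groups: "Separate 2 (group: low usage, high usage) x 3 (time: T0, T1, T2) repeated measures MANOVAs will be calculated". Neither names a covariate. The outcome is described as "within-subject changes on mean scores of developmental, activity and participation outcomes", without saying whether Bayley scores are raw or age-standardised. The use groups are to be formed from mean device-use data, and no cut-point is given.

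Only device order is randomised (Protocol 5.1): "randomization into two groups at each site will occur to determine which intervention participants will receive first". The split is 3 and 3 at each site, and no stratification by age is described. For Aim 1 the SAP states that "there are no previous data to conduct a power analysis on the potential change of developmental, activity and participation outcomes".

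**The concern.** The entry range is threefold, and toddlers at its two ends may well gain skills at different rates over 16 weeks. A stable difference in level between younger and older children drops out of a group-by-time contrast. A difference in rate of gain does not.

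This has different consequences in the two sets of models. Use groups are formed by what families do. If older (or younger) children drive more, the high-use and low-use groups differ in expected growth before any effect of driving, and the analysis cannot separate the two. That threatens validity. Order groups are formed by randomisation, so age-related growth only adds to the residual variation.

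There is also a smaller reporting matter. Age is continuous, and a table of age bands can hide a gap between order groups that is as long as the study itself.

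**Working it through.** **Inputs from the documents.** Age is 12 to 36 months (Protocol 2.2). At most 18 children complete (Protocol 2.7), at three sites (Protocol 3.1) with 3 and 3 per site (Protocol 5.1), so 9 v 9. Follow-up is 8 + 8 = 16 weeks, or 16/52 × 12 = 3.69 months.

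**The plan's own figure.** The only sample-size figure is 6 per group, for device-use minutes in Aim 2. With a difference of 1,060 − 171.4 = 888.6 and SD = √((783.8² + 206.1²)/2) = 573.1, the normal formula gives 6.53, so 7 (two-sided), or 5.14, so 6 (one-sided). It reproduces to within a child or so, but it does not bear on Aim 1, which has no power calculation.

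**Chance age gap between order groups.** Assume ages are uniform over 12 to 36 months.
- SD = 24/√12 = 6.93 months.
- SE of the difference in mean age = 6.93 × √(2/9) = 3.27 months.
- P(gap > 3.69 months) = 2 × [1 − Φ(3.69/3.27)] = 0.26.

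**Simulation** (4,000 replicates per setting, n = 18). Assume the expected 16-week gain is proportional to ln((age + 3.69)/age). The gain at 12 months is then ln(15.69/12)/ln(39.69/36) = 0.268/0.0976 = 2.75 times the gain at 36 months. Gains are scaled to mean 1, and other variation in change is normal with the SD shown. Scaled age-related growth has an SD of about 0.30 and a correlation with age of about −0.97. Linear age therefore explains about 0.082/(0.088 + SD²) of the variance of change. Change is regressed on group, with and without centred age. For the use comparison, use is correlated with age at r, has no effect on change, and is split at the median.

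| Other SD of change (× mean) | Share of variance explained by age | Order groups: CI width with age ÷ without | Use groups, no age term: type I error, r = 0.3 | r = 0.5 |
|---|---|---|---|---|
| 0.25 | 0.55 | 0.70 | 10.8% | 22.9% |
| 0.50 | 0.24 | 0.90 | 7.6% | 11.9% |
| 0.75 | 0.13 | 0.97 | 6.3% | 9.1% |
| 1.00 | 0.08 | 1.00 | 6.0% | 7.4% |

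With age in the model, type I error in the use comparison is 4.3-5.6% throughout.

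**Order comparison by a second route.** Let R² be the share of change-score variance explained by age (not given in the documents). Adjustment multiplies the variance of the group contrast by (1 − R²)(1 + 1/14) and reduces the error df from 16 to 15. Break-even for the variance is R² = 1/15 = 0.067. The difference detectable with 80% power (two-sided 0.05, no dropout) is 1.41 SD without age. With age it is 1.46 (R² = 0), 1.39 (0.10), 1.31 (0.20), 1.22 (0.30) and 1.03 (0.50). Simulated type I error of the unadjusted order test stays at 0.048-0.052.

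**The case against.** The strongest reply is that the documents cannot show that age matters for these outcomes. Protocol 5.1 describes the Bayley as norm-referenced, and if age-standardised scores are analysed, much of the age effect is already gone. No passage supports growth proportional to log age for the caregiver surveys. All GMFCS levels are eligible, so other variation in change may be large. At an other-SD of 0.75 to 1.0 times the mean change, 44-58% of simulated trials get a wider interval after adjustment. With 18 children in a pilot, the choice of covariates is open to judgement.

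Most of this stands for the order comparison, and it limits what can be claimed there. It does not settle the matter. The SAP leaves the Bayley score type open, and the CEDL and YC-PEM are not described as age-normed. Nor does the imprecision argument answer confounding in the use comparison, although the size there also rests on an assumed age-use correlation and an assumed median split.

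A reader might infer that omitting age biases the randomised order comparison or makes its test invalid. It does neither: chance age imbalance is already covered by the standard error. A reader might also take the sentence on categorical summaries as a rule for the models. It governs the descriptive table only; the modelling issue is the absent term.

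**Conclusion.** The point holds, with different weight in its two parts. In the low/high-use models, leaving age out allows confounding. Type I error is about 6-12% in moderate settings and up to 23% in the extreme one, against about 5% with age included. This assumes an age-use correlation of 0.3 to 0.5, age-dependent growth and scores that are not age-normed. In the randomised order models the issue is possible loss of precision only. The interval would narrow by 0-10% in moderate settings and by up to 30% if age dominates change, and would widen slightly if age explains less than about 7% of the variance of change. The documents do not show which of these applies, so a material loss of precision in the order comparison is not established.

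**What to change.** In the SAP:

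- **Data Analysis.** Summarise age at T0 in months (mean, SD, median, range), overall and by order group. The other characteristics can stay categorical.
- **Aim 1, use models.** Add age at T0, centred at the sample mean, and its interaction with time. Centring keeps the meaning of the time effect.
- **Aim 1, order models.** Add the same terms for outcomes analysed as scores that are not age-standardised (raw Bayley, CEDL, YC-PEM).
- **Score type.** State which Bayley scores are analysed.
- **Non-parametric branch.** A covariate and its time interaction do not carry over simply to the non-parametric equivalents. If that branch is taken, report the age-adjusted parametric model as a sensitivity analysis.

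The change needs SAP wording and one covariate that is already collected. It costs one error degree of freedom per model: 16 to 15 for a single change score, but proportionately more in a multivariate test. For example, if five Bayley domains over two time contrasts entered one MANOVA (an assumption), the denominator would go from 7 to 6. There is a slight loss of precision if age is unrelated to change: the detectable difference rises from 1.41 to 1.46 SD. Age adjustment does not remove other confounders of use, such as motor severity, so the low/high-use comparison remains observational.

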 \rightarrow If yes, briefly describe the urgency or deadline as well as the reason for it.

1.5 Objectives Using lay language, describe the purpose, specific aims, or objectives that will be met by this specific project. If hypotheses are being tested, describe them. You will be asked to describe the specific procedures in a later section.

If this application involves the use of a HUD "humanitarian" device: describe whether the use is for "on-label" clinical patient care, "off-label" clinical patient care, and/or research (collecting safety and/or effectiveness data).

The use of powered mobility devices for young children with cerebral palsy (CP) has been gaining traction, with evidence that the use of powered mobility at young ages complements (rather than detracts from) other interventions focused on more traditional mobility skills such as crawling and walking. This study will collect preliminary data (both numeric and opinion/perception data) to investigate device use patterns, caregiver perceptions, and developmental outcomes of children with CP as families are introduced to two early powered mobility interventions: the Permobil[®] Explorer Mini, and a modified ride-on toy car. Specific Aims include: Aim 1: Evaluate a powered mobility intervention to understand developmental, activity and participation outcomes of young children with CP. Aim 2: Compare the use patterns (frequency, duration, environment) and acceptability, feasibility, and intervention appropriateness of two powered mobility options: The Explorer Mini and a modified ride-on car.

1.6 Study design. Provide a one-sentence description of the general study design and/or type of methodology.

Your answer will help HSD in assigning applications to reviewers and in managing workload. Examples: a longitudinal observational study; a double-blind, placebo-controlled randomized study; ethnographic interviews; web scraping from a convenience sample of blogs; medical record review; coordinating center for a multi-site study.

This is a mixed-methods, randomized, counterbalanced AB crossover intervention study.

1.7 Intent. Check all the descriptors that apply to your activity. You must place an "X" in at least one box.

This question is essential for ensuring that your application is correctly reviewed. Please read each option carefully.

Descriptor

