Sample size justification: A power analysis based on preliminary data was used to determine the number of participants (*N*) necessary to satisfy statistical assumptions for the current study. Power was calculated from the results of the total time (minutes) a modified ride-on car was used between two groups: (1) Families who received bi-weekly support via in-person researcher visits (Mean minutes = 1,060; SD = 783.8), and (2) Families who received no support throughout a 3-month intervention period (Mean minutes = 171.4; SD = 206.1). Beta was set at .80 and alpha at .05 to calculate *N* which is standard practice. Analysis indicates that a sample of 6 participants in each group (modified ride-on cars, Explorer Mini) will produce meaningful treatment differences. This power analysis is appropriate given our hypothesis that the Explorer Mini will be used more frequently and more often than a modified ride-on car based on design features. Also, the above power analysis from previous data is based on between-group differences whereas the current study will examine within-group differences of use patterns between devices, resulting in less variability and greater likelihood of observing differences, if differences exist.

95% confidence intervals and mean number of driving sessions, mean duration (minutes) of driving sessions, and summed total duration (minutes) of driving sessions will be summarized by device type. Variable distributions will be examined to (1) identify appropriate response variable distributions, (2) screen for outliers, and (3) characterize patterns of data missingness. If assumptions for parametric statistics are met, we will use parametric statistics to examine within-subject effects. If assumptions for parametric statistics are not met, we will use the non-parametric equivalent of the planned analyses. A 2

(group: 1, 2) x 2 (time: T1, T2) repeated measures MANOVA will be calculated to determine withinsubject changes on the dependent measures of the mean number of driving sessions, mean duration (minutes) of driving sessions, and summed total duration (minutes) of device use. Significant differences will be followed-up with appropriate post-hoc analyses such as the Bonferonni correction to control for the type I error rate and determine where the significant differences exist.

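### Aim 1's time effect and low/high usage comparison cannot show an effect of powered mobility; the randomised device comparison lies unnamed in the group-by-time term

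*SAP*

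**What the plan says.** Protocol 1.5 words Aim 1 as "Evaluate a powered mobility intervention to understand developmental, activity and participation outcomes of young children with CP". Protocol 5.1 sets the design: "Participants will receive both powered mobility interventions, and randomization into two groups at each site will occur", the groups being which device comes first, three children each way at each site. Training on the first device takes place at T0, each phase lasts 8 weeks, and devices are removed at T2. On the changeover it says "No washout period between devices is indicated because both devices provide self-initiated mobility".

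The SAP (Aim 1) plans three analyses:

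1. A 2 (group) x 3 (T0, T1, T2) analysis: "repeated measures MANOVAs will be calculated to determine between- and within-subject changes on mean scores of developmental, activity and participation outcomes". Group is labelled 1 and 2 and not defined further.
2. The same model with low and high usage groups formed from mean device use: "We will use these stratified groups to run our analyses to determine if device use is related to developmental, activity and participation outcomes".
3. Visual analysis.

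Bonferroni follow-up is planned for the first two. The Protocol describes the Bayley as norm referenced, but the SAP does not say whether normed or raw scores are averaged. The Protocol gives no age reference for the CEDL or YC-PEM. Bayley administration is filmed and scored later. Section 10.7 on un-blinding is answered N/A, and masking of the scorer to visit or sequence is not described.

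**The concern.** Two of the planned Aim 1 tests can be significant when powered mobility does nothing.

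- **Time.** No child is ever observed without a device after T0. A T0-T2 change is device effect plus growth, and the design cannot separate them.
- **Usage.** The groups are set by what happened after baseline. Eligible children "have a medical diagnosis of CP with any level (I-V) of associated motor ability", or are at risk of CP, so more able children may drive more and also score higher.

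Under an aim worded as evaluating an intervention, either result could be reported as benefit. Meanwhile the comparison that randomisation does protect, one device against the other, has no stated Aim 1 estimate. With no washout, the pattern of any device difference at T2 is unknown, so the choice of contrast matters and should be made before the data are seen.

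**Working it through.** **Plan's own figure.** Aim 1 has none. The SAP's 6 per group is for minutes of use in Aim 2. It reproduces with a one-sided test (difference 888.6, pooled SD 573.1, d = 1.55; two-sided gives 7 or 8) and has no bearing on this point.

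**Inputs from the documents.** 18 children, three sites at 3 v 3, so 9 per sequence; ages 12-36 months; 2 x 8 weeks = 112 days; alpha 0.05 (stated for Aim 2).

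**Assumed.** One outcome with SD 1; equal correlation between visits (rho) of 0.70 or 0.85; ages spread evenly; the growth, ability and device effects given below.

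**Time test, zero device effect.** 112/30.44 = 3.68 months. SD of age = 24/sqrt(12) = 6.93 months. Ratio 0.531. If raw scores correlate r with age, growth g = 0.531r, which is 0.159, 0.266, 0.372 SD for r = 0.3, 0.5, 0.7. For linear growth the 2-df time test is noncentral F (2, 15 df) with noncentrality 9g²/(1 - rho):

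- g = 0.159, rho = 0.70: 0.76, significant in 10%.
- g = 0.372, rho = 0.85: 8.30, significant in 64%.

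Age-norming does not remove the problem. Norm growth in within-age SD is 0.531r/sqrt(1 - r²) = 0.167, 0.307, 0.520. If the children gain at half that rate, normed scores fall by 0.083, 0.153, 0.260 SD and the test is significant in 6-35%.

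A separate simulation with faster growth (0.2-0.5 SD per 8 weeks, measurement SD 0.5) gave 62-100% for the T0-T2 change. The size depends on assumed growth; the direction does not.

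**Usage split, zero device effect.** Simulated with skewed (lognormal) use, its spread taken from the SAP's supported car users ("Mean minutes = 1,060; SD = 783.8", so CV = 783.8/1,060 = 0.74), split at the mean, growth 0.37-0.5 SD varying by 50%:

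| Use-ability correlation | Usage main effect | Usage-by-time |
|---|---|---|
| 0 | 5% | 5% |
| 0.3 | 16-18% | 5-6% |
| 0.5 | 39-44% | 6-8% |

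So the main effect is the exposed term, and usage-by-time is little affected under these assumptions. If growth itself rises with ability and use correlates 0.7 with ability, comparing T0-T2 change between usage groups was significant in 31-50%.

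**Randomised device contrasts, 9 v 9.** Let d1 and d2 be the differences between sequences at T1 and T2, with d1 = 0.5 or 0.8 SD.

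- Sequence-by-period (phase 1 change minus phase 2 change, compared between sequences): difference 2d1 - d2, SD sqrt(6(1 - rho)), noncentral t on 16 df. Example, rho = 0.70, d1 = 0.5, d2 = 0: 1.0/1.342 x sqrt(4.5) = 1.58, power 32%.
- Group main effect: (d1 + d2)/3, SD sqrt((1 + 2 x rho)/3). The same example: 0.167/0.894 x sqrt(4.5) = 0.40, power 7%.
- Group-by-time: noncentral F on the two successive changes (2, 15 df).
- T1 ANCOVA (T0 and site as covariates, 13 df): simulated.

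| Difference at T2 | T1 ANCOVA | Group-by-time | Sequence-by-period | Group main effect |
|---|---|---|---|---|
| None | 26-82% | 23-83% | 32-92% | 6-9% |
| Half persists | 26-82% | 18-71% | 20-71% | 8-15% |
| All persists | 26-82% | 23-83% | 11.5-39% | 11-22% |
| Reverses | 26-82% | 59-99.9% | 61-99.9% | 5% |

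The median 95% CI half-width for the T1 difference is 0.73 SD (rho = 0.70) or 0.54 SD (rho = 0.85).

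**The case against.** The strongest reply is that the SAP already contains the randomised test. Protocol 5.1 defines two groups by device order. If the SAP's groups are those, group-by-time is sequence by visit, and follow-up tests are planned. This stands: the table puts that term about level with T1 ANCOVA in two cases, lower if half the difference persists, and well ahead on reversal. What is missing is the definition of group, a named estimate and a CI.

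The documents are also modest in tone. They speak of preliminary data and a pilot, and the usage analysis is worded as association. That is fair, but significance tests with Bonferroni follow-up are still planned under an aim of evaluation.

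A reader might infer four stronger things that the documents do not support:

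- That the SAP names no device comparison anywhere. Aim 2 states one for use patterns, with 95% CIs summarised by device.
- That the SAP itself claims a causal effect of powered mobility. Its causal phrase is "potential change of developmental, activity and participation outcomes as a result of using different powered mobility devices", which concerns different devices and sits in a sentence on why there is no power analysis.
- That T1 ANCOVA should be the only primary contrast. In a crossover that discards phase 2. If an outcome follows the device currently in use, which is plausible for caregiver-reported participation, the difference reverses at T2 and ANCOVA is much the weaker test.
- That the Bayley will hit a norm floor, or that a second scorer is needed. The documents give no basis for either.

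**Conclusion.** The point holds for Aim 1 and should be corrected. That the time effect and the usage comparison cannot show an effect of powered mobility follows from the design alone: no device-free child or period, and only order randomised. This part is firm. Norm-referenced scores would take out only the norm sample's average growth.

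The percentages are illustrative. They rest on assumed growth, correlations, age spread and ability-use links, and on one outcome where the SAP plans several. The spread of use comes from car-only families with bi-weekly in-person support over 3 months, not from this trial's two virtual check-ins per phase.

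The device comparison is present but under-specified. It sets device against device, so even a clear result would not show that powered mobility works. With a CI of about +/-0.54 to 0.73 SD, a null result would not show that the devices are equal.

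**What to change.** 1. State in the SAP that Aim 1 time and usage results (main effect and usage-by-time) are descriptive or associational and are not evidence of a powered mobility effect.
2. Define group as randomised device order. Base Aim 1 device inference on group-by-time, not on the group main effect, which averages in T0. Report the T1 difference between sequences, adjusted for T0 and site, with a 95% CI as the carryover-free estimate, and the sequence-by-period contrast beside it. State the trade-off: T1 ANCOVA has the same power whatever happens at T2; sequence-by-period is stronger if the sequences coincide again or reverse at T2 and much weaker if the difference persists. State also that both compare device with device and that a null result does not show equal devices.
3. Report age-normed Bayley scores beside raw scores, with change descriptive on both. A child entering at 36 months finishes by about 36 + (112 + 10)/30.44 = 40.0 months, allowing the 5-day grace in each phase, which is within the test's 42-month range.
4. Code and shuffle the Bayley videos before the existing scorer sees them, so that visit and sequence are not shown. State that the CEDL and YC-PEM are unmasked.

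**Cost.** SAP wording, a little extra analysis and some file handling; no new arm, visit or second scorer. The Aim 1 conclusion becomes narrower. Masking is only partial: the person administering the Bayley knows the visit, children visibly age over 16 weeks, and team members may perform all procedures. Scoring within site avoids moving identifiable video.
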